**MEDICAL PROTOCOL (HRP-590)****PROTOCOL TITLE: VISUAL SURROUND SUPPRESSION UNDER PSILOCYBIN****VERSION DATE: May 18, 2023**

will have either an RN (Clinical Research Unit staff) or MD degree, with experience managing behavioral emergencies, including de-escalation, calming and preventing elopement. The other monitors that do not have an RN or MD have extensive field experience providing support for psychedelic crisis situations at festivals and other events where people take recreational psychedelics and come to the facility designated for people seeking out psychological support during a psychedelic-induced crisis. Other monitors that will serve as the second person will be trained accordingly. We will call these monitors “sitters” and they will be positioned near the participant during the portion of the session where they are laying down with eye shades and listening to music. Sitters will be trained in fundamental guidelines for helping people navigate a psychedelic experience, adapted from models of harm reduction services offered at festivals for people having a difficult experience. Examples include instances where the participant arises from their headphones and eyeshades, and the sitters will engage with the participant using a supportive and non-directive approach, maintaining an empathic presence, while encouraging them to maintain their focus inward in between testing sessions for the duration of the experience. At least one sitter will be present at all times to be able to respond to verbal and non-verbal behavior with communication or supportive touch. Supportive touch will be discussed during the consent and enrollment process. We will ask the participants what their comfort level is for supportive touch, while ensuring that extensive touch, such as hugging or cuddling will not be allowed, even if requested. We will simply, if they consent before the dosing session, provide a hand on the back, arm, or hold their hand during challenging or stressful parts of the experience. We will ask for their permission anytime a supportive touch seems warranted, and will only touch if they have agreed beforehand during the consent process, and with a verbal confirmation during the dosing experience. The consent and extent of supportive touch will be assessed and agreed upon with the participant during enrollment, and confirmed on the day of testing. We will ensure that we have an MD physician present in a nearby room in the CRU for the duration of each dosing session to monitor safety and guide/provide interventions should medical situations arise that require the physicians care.

**Schedule for checking vital signs.** In order to monitor participant safety during the dosing sessions, we will monitor their heart rate and blood pressure throughout the session. Heart rate will be measured with a pulse oximeter and blood pressure will be measured with a pressure cuff. We will measure vital signs 15 minutes before dosing, and then again at 15, 30, 45, 60, 90, 120 minutes and three, four, six and eight hours after dosing, with an allowable time deviation of +/- 5 minutes to account for any delays during the day for checking vitals. In the event of a hypertensive emergency where blood pressure rises above 180/120mmHg (systolic/diastolic), and they are experiencing other associated symptoms of potential organ damage, including chest pain, shortness of breath, back pain, numbness/weakness or difficulty speaking, then we will stop the session and call a code 21, per our crisis communication plan (see appendix D). In the unexpected event that we do have a participant with a hypertensive emergency (Johnson et al 2008), we will immediately administer sublingual clonidine while we wait for emergency personnel to arrive. Our physicians do not feel administering an IV injection would be wise, as in the altered state of consciousness, this may exacerbate their symptoms, as would having an

MEDICAL PROTOCOL (HRP-590)

PROTOCOL TITLE: VISUAL SURROUND SUPPRESSION UNDER PSILOCYBIN

VERSION DATE: May 18, 2023

IV catheter placed for the duration of the dosing session. The emergency room is in the building adjacent to the Clinical Research Unit, accessible via underground tunnels, and calling a code 21 will alert emergency personnel to come to our dosing room to treat the participant and transfer them to the emergency department.

Participants experience will be interrupted in order to conduct the EEG and behavioral testing during the peak of the experience (starting 2 hours after ingestion of study drug). EEG will be administered by trained study staff using a dry-electrode wireless headset paired to a computer and monitor that will be used to administer the surround suppression task.

**EEG.** We will use an EEG paradigm to measure responses to the presentation of simple visual stimuli (e.g., black and white stripes) presented on a computer. Subjects will be asked to respond to the appearance of the visual stimuli via button press (Figure 2). We will record EEG signals from multiple scalp sites (electrodes) using a 21-channel dry electrode EEG system. Subjects will be asked to keep their eyes focused on the screen during the task, and to remain as still as possible to ensure higher data quality. Subjects will be monitored by study staff (in the testing room) during the experiment. EEG data using a dry electrode system will be collected in the CRU testing room during baseline and on dosing session days for consistency of environment/setting. EEG sessions will be conducted by study staff that are trained to collect EEG data.

**Psychophysics behavioral task.** We will use visual behavioral tasks to assess perceptual functioning and learning in human subjects. Subjects will see a series of simple images (e.g., gray stripes) presented on a computer screen and will be asked to make basic judgments about their appearance (e.g., report which of the two images appears stronger). Subjects will make responses by pressing buttons on a response device (e.g., keyboard). Subjects will be asked to keep their head position stable on a chin rest and to focus their eyes at the center of the screen during the task. Behavioral data will be collected in subject testing space located in the CRU.

[figure not shown]
**Subjective experience questionnaires at end of dosing session.** Once the subjective effects of the study drug have subsided, prior to being discharged from the CRU, we will administer subjective experience questionnaires (5D-ASC, RMEQ-30, EDI, EBI) related to how their experience was during the day on the study drug.

**Assessment of participant before discharge from dosing session.** Prior to being released to a trusted family member or friend at the end of the session, we will assess the participant to make sure they are safe to leave. We will do a physical and mental health assessment, including measuring vital signs, ECG, mental health status and responses to questions about thought processes, such as suicidal ideation with the CSSRS or other concerning symptoms (see appendix E). If the participant is displaying symptoms that need to be continually monitored, we will discuss with the clinical staff whether to admit them for follow-up care. Additional follow-up care that is needed will be billed to the participants health insurance.

MEDICAL PROTOCOL (HRP-590)

PROTOCOL TITLE: VISUAL SURROUND SUPPRESSION UNDER PSILOCYBIN

VERSION DATE: May 18, 2023

**Figure 2. Schematic of surround suppression task (Schallmo and Murray, 2016)**

**Safety.** Participants will be instructed to immediately inform the study team if any serious concerns arise with their health during the study. The team will assess all adverse effects, including frequency, severity and relationship to study drug. For participants that experience adverse psychological effects, including, but not limited to suicidal ideation, likely or probably related to study drug, the participant will be instructed to speak with a mental health professional to assess their status, either by Drs. [name] or [name] (clinical Co-Investigators). Participants will be given a list of phone numbers to call in the event that they are experiencing distress, such as suicidal ideation, including the study investigator at the telephone number listed on the first page of the consent forms, and instructed that if they feel they are crisis, that they can call 911 and/or a Nationwide Suicide Hotline that is answered 24 hours a day with a skilled, trained counselor. One example is the National Suicide Prevention Lifeline at [name].

Participants will be pre-prescribed antipsychotics and antianxiety medications in case the participants or the study staff want to stop the psilocybin experience with these pharmacological interventions. These costs will be paid for by the study funding. Some antipsychotics, like Risperidone, are able to bind to 5HT2A to block the activation of this receptor in the presence of psilocybin, whereas anti-anxiety medications, such as benzodiazepines, will help calm down the participants should they become agitated or too

**MEDICAL PROTOCOL (HRP-590)**

**PROTOCOL TITLE: VISUAL SURROUND SUPPRESSION UNDER PSILOCYBIN**

**VERSION DATE: May 18, 2023**

anxious during the testing session. See Appendix D for more information on the crisis communication plan.

At the end of each experimental session (8 hours post-drug administration), participants will be released into the care of a trusted friend or family member to drive them home. (Prior to dosing on the day of each experimental session, participants will be required to confirm that they have arranged for reliable transportation).

**Visits 3 and 5**

**Digital Journal.** Throughout the study, participants will also be asked to keep a digital journal that will be submitted after each dosing session (**Visit 3 and Visit 5**), and at the end of the study (**Visit 7**) to document their qualitative and subjective experience for content analysis. Within 1 week after their dosing session, participants will be asked to write for 30-60 minutes to describe the content of their experience, and any reflections or interpretations they derived from the experience to help determine the subjective information of their drug experience. These will be collected in a REDCap form (see Appendix F) and sent out to participants via email or text after completion of the dosing session, and a follow-up email or text towards the end of the week if they have not completed the form.

**Debriefing session.** One day following each dosing session (Visits 3a and 5a), study staff will meet with the participant for about 60 minutes (either in person at CMRR prior to MRI, or remotely over Zoom) to discuss the dosing session the previous day, and debrief on anything they want to discuss or process with the study staff.

**Blood Draws.** All blood draws will be performed by the clinical staff onsite, and blood samples will be stored at the Cytokine Reference Lab on campus for cytokine assays, and serum chemistry will be processed by Fairview. Samples will be collected at baseline (**Visit 1**) and again at **Visit 3 (a,b,c)** and **Visit 5 (a,b,c)**.

**MRI.** See CMRR section below (5.5).

All neuropsychiatric, baseline and follow up testing will be conducted in the ARC (or Zoom, if appropriate), and all fMRI sessions will be collected at CMRR. All dosing sessions and EEG data collection will be performed in the CRU. The study coordinator will greet each participant upon arrival, and escort them to the different locations for data collection and testing.

MEDICAL PROTOCOL (HRP-590)

PROTOCOL TITLE: VISUAL SURROUND SUPPRESSION UNDER PSILOCYBIN

VERSION DATE: May 18, 2023

Participants will be monitored at each visit for adverse events (*Zoom option*), including for suicidal thoughts, and given at least 2 weeks between dosing/testing sessions for drug washout. After completion of final dosing sessions, participants will undergo follow up assessments at 2 weeks (**Visit 6**) and 2 months after the final dosing session for study closeout (**Visit 7**).

## MEDICAL PROTOCOL (HRP-590)

PROTOCOL TITLE: VISUAL SURROUND SUPPRESSION UNDER PSILOCYBIN

VERSION DATE: May 18, 2023

## Schedule of Events

|  | Enrollment and Baseline Testing
Visit 1* | Dosing Session
Study Visit 2^
(Condition 1) | Study Visit 3#
(Follow up and Washout) | Dosing Session Study
Visit 4^
(Condition 2) | Study Visit 5#
(Follow up and Washout) | Study Visit 6
(Follow up) | Study Visit 7
(follow up and close out) |
|--|---|---|---|---|---|------------------------------|--|
| COVID+ and other time deviations for Visit Window Adjustment | +/- 7-14 days \$                 | +/- 7-14 days \$                       | +/- 7-14 days \$               | +/- 7-14 days \$                       | +/- 7-14 days \$               | +/- 7-14 days \$  | +/- 7-14 days \$                |
| Time Point   | Week 1                                      | Week 2  | Week 3                                    | Week 4  | Week 5                                    | Week 6                       | Week 12                                    |
| Informed consent   | X   |   |   |   |   |                              |  |
| Demographics   | X   |   |   |   |   |                              |  |
| Medical history  | X   |   |   |   |   |                              |  |
| Psilocybin or Placebo  |   | X   |   | X   |   |                              |  |
| Concomitant medication review                                | X   | X   | X   | X   | X   | X                            | X  |
| Physical exam (including height and weight)                  | X   | X   | X   | X   | X   | X                            | X  |

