**Neuroimaging Procedures.** All brain imaging will be completed at the CMRR on a 3T whole body Siemens MAGNETOM scanner (Siemens Medical Solutions, Erlangen, Germany) using a standard Nova coil. We will take a series of scans during a single session to collect structural and functional fMRI data. Data will be collected from participants during baseline assessment and within 24 hours following each dosing day, and again at 3-4 days and 7 days after each dosing session for a total of 7 scans per participant. After an initial structural scan, we will collect resting state fMRI to test changes in BOLD signal in brain networks known to be impacted by psilocybin and other 5HT2A receptor mediated psychedelics, including the default mode network (Carhart-Harris et al., 2014). Heart rate and respiratory rate data will also be collected during the scan to account for artifacts that may confound results during resting state scan. We will then perform a series of task-based scans using the same visual tasks tested during the EEG dosing session (*SEE Psychophysics section under Visits 2 and 4*). We will then perform a diffusion-weighted MRI (dMRI) scan to look for changes in structural connections in white matter, which has been shown previously in animal models with serotonergic psychedelics (Ly et al., 2018). Data will be processed using standard software packages (e.g., the FMRIB Software Library (FSL - FslWiki)), which is an open-source software library that contains tools for statistical analysis and image processing for MRI brain imaging data).

The same study procedures, except consent, demographics and medical history will be performed at Visits 3, 5, 6 and 7. Pregnancy test will be collected on Visit 1, 2, 3, 4, and 5. EEG and psychophysics will be collected on visits 2, 4, and 6, and fMRI will be collected on Visits 1, 3, and 5. Regarding blood draws, two separate tubes of blood will be collected at Visits 1, 3, and 5 for serum chemistry and cytokine assays.

## VISITS 2 and 4

MEDICAL PROTOCOL (HRP-590)

PROTOCOL TITLE: VISUAL SURROUND SUPPRESSION UNDER PSILOCYBIN

VERSION DATE: May 18, 2023

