## MEDICAL PROTOCOL (HRP-590)

## PROTOCOL TITLE: VISUAL SURROUND SUPPRESSION UNDER PSILOCYBIN

VERSION DATE: May 18, 2023

|   | Enrollment and Baseline Testing Visit 1* | Dosing Session Study Visit 2^ (Condition 1) | Study Visit 3 (Follow up and Washout) | Dosing Session Study Visit 4^ (Condition 2) | Study Visit 5 (Follow up and Washout) | Study Visit 6 (Follow up)   | Study Visit 7 (follow up and close out) |
|---|--|---|---------------------------------------|---|---------------------------------------|-----------------------------|---|
| COVID+ Visit Window Adjustment                        | +/- 7-14 days \$              | +/- 7-14 days \$                 | +/- 7-14 days \$           | +/- 7-14 days \$                 | +/- 7-14 days \$           | +/- 7-14 days \$ | +/- 7-14 days \$             |
| Vital signs (including heart rate and blood pressure) | X  | X #                              | X                                     | X #                              | X                                     | X                           | X                                       |
| ECG   | X  | X   |                                       | X   |                                       |                             |   |
| Serum Chemistry and cytokine testing a     | X  |   | X                                     |   | X                                     |                             |   |
| Pregnancy test b                           | X  | X   | X                                     | X   | X                                     |                             |   |
| Alcohol intoxication screen c              |  | X   |                                       | X   |                                       |                             |   |
| Adverse event review and evaluation                   | X  | X   | X                                     | X   | X                                     | X                           | X                                       |
| Neurophysiology/EEG                                   | X  | X   |                                       | X   |                                       | X                           |   |
| MRI   | X  |   | X                                     |   | X                                     |                             |   |

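### The +/- 7-14 day visit allowance also covers Visits 3 and 5, whose MRI scans are due 1, 3-4 and 7 days after dosing, so its smallest shift exceeds the 6-day span of the set

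*Combined protocol and SAP*

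**What the plan says.** The Schedule of Events prints +/- 7-14 days in all seven visit columns. On its first page the row is labelled "COVID+ and other time deviations for Visit Window Adjustment"; on the later pages, including the one with the MRI and blood rows, the label is "COVID+ Visit Window Adjustment". The footnote to the row refers to changing quarantine guidance and to scheduling overlap between Visits 1 and 2. It states that the adjustment does no harm to data integrity or quality. It sets no separate limit for Visits 3 and 5.

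Section 5.2, Neuroimaging Procedures, places the post-dose scans "within 24 hours following each dosing day, and again at 3-4 days and 7 days after each dosing session". With the baseline scan, the plan counts seven per participant. The Schedule of Events footnote on Visits 3 and 5 spreads each over three separate days shortly after dosing, for repeated fMRI and blood draws. For blood, section 5.2 says "Samples will be collected at baseline" and then at Visits 3a-c and 5a-c. Visits 3a and 5a are set one day after the dose. The two dosing sessions must be at least two weeks apart.

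Section 15.3 tests resting-state networks at baseline and at 1, 3 and 7 days after each compound. It has no rule for a scan taken off its day.

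**The concern.** An allowance of one to two weeks can be harmless for a visit placed only by calendar week. It is not harmless for measures defined by a few days since dosing. If the row is followed as printed, a scan that has missed its intended time altogether is still in window, and the plan does not say whether it then counts as the day 1, 3 or 7 point.

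The stake is the post-dose time course. A late scan counted at its nominal day blurs the contrast between day 1, day 3 and day 7 within each drug. In a crossover there is a further cost: a Visit 3 scan that slips far enough is taken after the second drug but carried as first-drug data.

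**Working it through.** **Inputs.** Post-dose scan days 1, 3-4 and 7, and seven scans in total (section 5.2, Neuroimaging Procedures). Allowance +/- 7-14 days (Schedule of Events). Minimum gap between doses 14 days (section 5.2, Visits 3 and 5). Two readings are assumed: the 24-hour limit is taken as day 1, and both 7 and 14 days are shown because the plan does not say when each applies.

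**Reproducing the plan's count.** One baseline scan plus three after each of two doses: 1 + 2 x 3 = 7, which matches. Visits 3 and 5 therefore hold three scans each, so 7 - 1 = 6 of the 7 scans per participant come under the row.

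**Span against shift.** The set runs from day 1 to day 7: 7 - 1 = 6 days. The smallest printed shift is 7 days, and 7 > 6.

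**Shifting the set with the dose date fixed.**

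| Shift | First scan | Second scan | Third scan |
|---|---|---|---|
| -14 | day -13 | days -11 to -10 | day -7 |
| -7 | day -6 | days -4 to -3 | day 0 |
| none | day 1 | days 3-4 | day 7 |
| +7 | day 8 | days 10-11 | day 14 |
| +14 | day 15 | days 17-18 | day 21 |

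- Minus side: at either printed limit the whole set falls before or on the dosing day, which is impossible for a post-dose measure.
- +7: the first scan, on day 8, falls after nominal day 7. The third, on day 14, falls on the earliest permitted date of the second dose.
- +14: all three scans fall after day 14. If Visit 4 has kept its date, every Visit 3 scan follows the second drug.

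**Scale of a workable tolerance.** The gaps between neighbouring points are 3 - 1 = 2 days and 7 - 4 = 3 days. A symmetric tolerance that keeps the points distinct must be under 2/2 = 1 day at the first gap and 3/2 = 1.5 days at the second.

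**The case against.** The strongest reply is that the specific text governs. The scan days are stated plainly in section 5.2, the row sits beside calendar-week labels, and its minus side cannot apply literally to a post-dose scan. On that view a dosing visit and its follow-up move together and the days since dose are preserved. This may be what was intended, but the plan does not say it, and Visits 3 and 5 carry their own entry in the row. Nor can it cover a participant who tests positive after dosing: the dose date is then fixed and only the follow-up can slip.

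A second reply is that the allowance is a quarantine contingency, as the footnote and the later row labels suggest. That narrows how often it would be used. It does not remove the first-page label, which extends to other deviations, and neither reason in the footnote supports the claim of no harm for dose-anchored scans.

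A third reply is that section 15.3 already defines its points by days after exposure. That stands. What is missing is the handling of a scan taken off its day.

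Four stronger readings might be inferred, and the documents do not support them:

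- **Shortened washout.** The minus side at Visit 4 might seem to shorten it, but participants are to be "given at least 2 weeks between dosing/testing sessions for drug washout", and that floor blocks it.
- **A drifting Visit 6.** Section 5.2 already sets Visit 6 at two weeks after the final dosing session.
- **Three time points collapsing into one.** This needs a separate window for each sub-visit. The row gives one per visit, and the footnote requires three separate days; under a block shift the points stay distinct.
- **A variable lag between cytokines and EEG.** Section 15.1 does not say which draw would be related to which EEG recording.

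**Conclusion.** The point holds and is minor. As printed, the rule accepts a day-1 scan on day 8 or day 15, and a first-drug scan on or after the earliest second-dose date. The footnote's assurance about data quality does not hold for Visits 3 and 5.

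This rests on two conditions: that the dose date is fixed while the follow-up slips, and, for the crossover consequence, that Visit 4 does not move later as well. The scan days are stated outright. The corresponding blood-draw days are inferred from sub-visits a-c and the footnote.

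A reader might multiply up to 40 x 6 = 240 of 40 x 7 = 280 scans affected. That counts scans exposed to the rule, not scans delayed, and the documents give no frequency of delay. Nor does the point reach the main test: the section 3 endpoints are psychophysics and EEG, and the acute 2-hour measurements do not depend on when Visits 3 and 5 take place.

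**What to change.** In the Schedule of Events:

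- Exempt Visits 3a-c and 5a-c from the row. Anchor them to the actual dose date at the times already in section 5.2, with a narrow tolerance for day 7, for example days 6-8. The plan already does this for vital signs, "with an allowable time deviation of +/- 5 minutes to account for any delays during the day for checking vitals".
- State that if a dosing visit moves, its follow-up visits move with it.
- Limit the footnote's assurance to visits without dose-anchored measures.

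In section 15.3:

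- Analyse fMRI and blood outcomes by actual days since dose.
- Do not count an out-of-window measure as the day 1, 3 or 7 point.
- Do not count Visit 3 measures taken after the second dose as first-drug data.

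The cost is a wording amendment, with no added visits, scans or participants. A few late scans leave the nominal-day comparison but stay usable by actual day.
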